7.3.4 Sensitivity analysis for missing data

We expect very low missingness of data in our results. We will explore the demographic and clinical characteristics comparing persons with full and incomplete follow-up, and try to define the mechanism of missingness with the input of study staff about clinical operations. This experiential input is necessary, because there is no data-driven mechanism to decide on non-ignorability of missing data. For Missing Not At Random sensitivity analysis, we will use multiple imputation methods to test the robustness of our results.

7.3.5 Qualitative analysis

Analysis. Transcripts of audio-recordings from in-depth interviews will be uploaded into MAXQDA software²² for the purposes of coding and analysis. Our approach to the qualitative data will involve thematic analysis and employ both inductive and deductive coding techniques.^{23,24} We will first develop an *a priori* code book that reflects key analytic dimensions of the RE-AIM framework. New themes that emerge from the data will be analyzed through a grounded theory approach, allowing for themes to emerge and ensuring that the knowledge assembled from the observational data is not subjected to the themes solely established through the in-depth interview guide. Qualitative analysis will proceed by first exploring broad patterns and experiences of patients, peers, drug treatment clinic leadership and staff, and then assessing possible similarities and differences in experiences between staff (including different ages, sex, and level of training) and the 5 different sites. Two coders will conduct open coding on three transcripts to develop initial coding schemes. After discussion and development of a combined draft scheme, two more interviews will be coded, and these will be further discussed and inform a final coding scheme which will be developed. Through weekly meetings, a team approach to data analysis will be employed, whereby different analysts provide feedback on emerging interpretations and check emerging categories against the raw data. In this way, an "audit trail" will be used to help ensure trustworthiness of findings, gather input from multiple perspectives, and enhance reliability.

Mixed methods. The qualitative data will provide context to the quantitative data and in-depth understanding of barriers and facilitators to program implementation in the local context. We will merge and integrate quantitative and qualitative data. The qualitative themes will be compared to survey results, combined and jointly displayed. We will create a matrix relating qualitative themes to quantitative variables. Findings will inform future programming efforts.

8 ETHICS

8.1 Independent Ethics Committee/Institutional Review Board (IEC/IRB)

The JHM IRB will provide IRB oversight for all domestic sites. Expert review of the research protocol is carried through the work of the JHM IRB to ensure that research is well designed and likely to yield generalizable knowledge, and that risks are both commensurate with benefit and accurately disclosed to research participants. This protocol, the ICF, and any subsequent modifications will be reviewed and approved by the JHM IRB or ethics committee responsible for oversight of the study. A signed consent form will be obtained from the participant (or legal representative or person with power of attorney for participants who cannot consent for themselves). The consent form will describe the purpose of the study, the procedures to be followed, and the risks and benefits of participation. A copy of the consent form will be given to the subject, or legal representative and this fact will be documented in the participant's record.

8.2 Ethical Conduct of the Study

The study will be conducted in accordance with the protocol, ICH guidelines, applicable regulations and guidelines governing clinical study conduct and the ethical principles that have their origin in the Declaration of Helsinki. Responsibilities of the Investigator are specified in Appendix D.

8.3 Subject Confidentiality

To protect subjects' confidentiality, all subjects and their associated samples will be assigned numerical study identifiers or codes.

8.4 Johns Hopkins University Transplant Oncology and Infectious Diseases Clinical Research Center (TOID CRC)

8.4.1 Protocol and Consent Version Control

The TOID CRC will maintain protocol and consent version control. The umbrella protocol will not be modified by any site other than the TOID CRC. All amendments and other pertinent protocol information are sent to the participating sites via email, as a PDF document, after approval by JHM IRB. The TOID CRC will maintain a Regulatory Database for this study that will record the protocol and informed consent version, JHM IRB approval and expiration date, participating site distribution date and confirmation of receipt via the Protocol Signature Page that will be signed and dated by the site's Principal Investigator and returned to the TOID CRC.

8.4.2 Data Collection and Management

Study data will be entered via eCRFs using the REDCap EDC system. The REDCap EDC is a secure web-based electronic data capture system. Each person entering data in the EDC system must complete a training. After verification of appropriate training, the Data Center will issue a unique username and password. The username and password will create an audit trail each time data is entered. Routine remote and/on-site monitoring will be conducted to verify timely and accurate entry of data.

8.4.3 Protocol Events and Deviations

Sites will report all SAEs to the TOID CRC by entering the SAE directly into REDCap. When the site enters a SAE into the study database, an automatic email will be generated and sent to the TOID CRC Safety Contact. The TOID CRC will then review the case to ensure completeness and clarity, and confirm seriousness and attribution. In addition, all sites will follow their local reporting requirements. Domestic sites will also be responsible for reporting protocol events and/or protocol deviations that meet JHM IRB prompt reporting directly to the JHM IRB:

https://www.hopkinsmedicine.org/institutional_review_board/guidelines_policies/organization_policies/prompt_reporting_policy.html

8.4.4 Annual Enrollment Data

Annual enrollment data will be directly reported to the JHM IRB by the TOID CRC.

9 SOURCE DOCUMENTS AND CASE REPORT FORM COMPLETION

The Investigator is responsible for ensuring the accuracy, completeness, legibility, and timeliness of the data reported. All source documents should be attributable, legible, contemporaneous, original, accurate, and complete to ensure accurate interpretation of data. Clinical site monitoring is conducted to ensure that the rights and well-being of human subjects are protected, that the reported trial data are accurate, complete, and verifiable, and that the conduct of the trial is in compliance with the currently approved protocol, ICH GCP, and applicable local regulatory requirement(s).

10 DATA QUALITY ASSURANCE

Sponsor will ensure that the clinical trial is conducted with a quality management system that will define quality tolerance limits in order to ensure human subject protection and reliability of study results. Data will be generated, documented and reported in compliance with the protocol, ICH GCP, and applicable regulatory requirements.

11 COMPLETION OF THE STUDY

The end-of-study is defined as the date of the last subject's last visit.

APPENDIX A. SCHEDULE OF EVENTS (ALL PARTICIPANTS)

	Recruitment Screen	Day 0	Treatment Day 1	Treatment Week 4	End of Treatment -0d/+30d	Post-Treatment Week 12 -14d/+30d	Post-Treatment Week 24 -14d/+30d	Post-Treatment Week 36 -14d/+30d	Early D/C Visit
Eligibility Review ^a	X	X							
Vital Signs ^b		X							
Demographics		X							
Medical History		X							
Concomitant Medications ^c		X			X				
Randomization		X							
Referral to HCV Treatment (SOC Arm Only)		X							
AE/SAE Collection ^d			→	→	→				
Laboratory Testing									
HBsAg		X							
Pregnancy Test ^e		X							
CBC ^f		X							
HCV RNA ^g		X			X	X		X	X
CMP		X			X	X			X
Urine Toxicology Screen		X			X	X	X	X	
Dried Blood Spot		X			X	X	X	X	X
Surveys/Questionnaires									
Study Survey		X			X	X	X	X	
PRO/QOL Measures		X			X	X	X	X	
Intervention Arm Only									
Peer Contact ^h		X	→	→	→	→			X
Study Drug Dispensation ⁱ			X	X					

^aIncluding documentation of HCV infection (antibody) and treatment history.

^bIncluding height, weight, temperature, pulse, respiratory rate, and blood pressure.

^cAll medication (including supplements and over-the-counter) will be collected.

^dAE/SAE collection starts with initiation of DAAs, continues through 30 days after last DAA dose.

^eFor all participants of childbearing potential. Urine or serum test.

^fWith or without differential.

^gCLIA certified.

^hPeer contact to occur weekly and as needed between visits until SVR 12. Contact can be in-person, via phone, or video.

ⁱStudy drug can be dispensed in smaller amounts more frequently if participant is unable to maintain 4-week supply at home.

APPENDIX B. SCHEDULE OF EVENTS (PARTICIPANTS WHO DO NOT START HCV TREATMENT BY WEEK 12 AFTER RANDOMIZATION IN EITHER ARM)

For participants who have not initiated treatment by Week 12 after randomization, complete the following.

	Week 12 after randomization -14d/+30d	Week 24 after randomization -14d/+30d	Week 36 after randomization -14d/+30d	Week 56 after randomization -14d/+30d
Laboratory Testing				
Urine Toxicology Screen	X	X	X	X
Dried Blood Spot	X	X	X	X
HCV RNA ^e		X		X
Surveys/Questionnaires				
Study Survey	X	X	X	X
PRO/QOL Measures	X	X	X	X
Rescreen for SOC Participants to Rollover to Intervention Arm				
Eligibility Review		X		
Vital Signs ^a		X		
Concomitant Medications ^b		X		
HBsAg		X		
Pregnancy Test ^c		X		
CBC ^d		X		
CMP		X		
Peer Contact ^f		→		

^aIncluding height, weight, temperature, pulse, respiratory rate, and blood pressure.

^bAll medication (including supplements and over-the-counter) will be collected.

^cFor all participants of childbearing potential. Urine or serum test.

^dWith or without differential.

^eCLIA certified.

^fParticipant will meet with peer on date of rescreen. If participant is still eligible for rollover to Intervention Arm after rescreening labs result, peer contact to occur weekly and as needed between visits until SVR 12. Contact can be in-person, via phone, or video.

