3.3 Secondary Endpoints

- 1) HCV treatment completion: Proportion of those initiating treatment who complete HCV treatment defined as taking more than 90% of prescribed treatment course by expected end of treatment date.
- 2) SVR 12: Proportion of participants with HCV RNA <15 IU/ml between 10 and 36 weeks after end of treatment in each randomization arm.
- 3) Time to HCV treatment initiation after randomization.

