Participants in the standard of care arm who do not initiate HCV treatment within 6 months (24 weeks) after randomization and still meet study eligibility criteria upon rescreen will be offered HCV treatment at the OTP site via rollover to the Intervention Arm.

Any participant that does not clear HCV infection will be linked to repeat HCV treatment and care at an offsite HCV treatment location through standard of care. There are approved regimens available to treat patients who do not achieve cure with first line treatment.

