6.2.2 Medical Complaints/Adverse Events and Serious Adverse Events

An AE is defined as any untoward medical occurrence in a subject or clinical investigation subject administered a pharmaceutical product and which does not necessarily have a causal relationship with this treatment. An AE can therefore be any unfavorable and unintended sign (including an abnormal

laboratory finding), symptom, or disease temporally associated with the use of a medicinal (investigational) product, whether or not the event is considered causally related to the use of the product.

An AE can result from use of the drug as stipulated in the protocol or labeling, as well as from accidental or intentional overdose, drug abuse, or drug withdrawal. Any worsening of a pre-existing condition or illness is considered an AE. Worsening in severity of a reported AE should be reported as a new AE. Laboratory abnormalities and changes in vital signs are considered to be AEs only if they result in discontinuation from the study, necessitate therapeutic medical intervention, meets protocol specific criteria (see Section 6.3 regarding toxicity management) and/or if the investigator considers them to be AEs.

Adverse event reporting will follow the requirements outlined below. Adverse events will also be recorded and tracked in a safety monitoring database by the investigators. Serious adverse events (SAEs) will be reported to the Institutional Review Board according to IRB guidelines and to AbbVie via the Johns Hopkins University Transplant Oncology and Infectious Diseases Clinical Research Center (TOID CRC).

All Grade 3 or higher and all SAEs related to the use of GLE/PIB in intervention arm or prescribed DAA course in SOC arm will be collected. Thus, AEs and SAEs will only be collected from the time of first DAA dose to 30 days after completion of DAA course.

All Grade 3 or higher AEs and all SAEs will be reviewed by the principal investigator as they occur in a timely manner. All AEs related or possibly related to GLE/PIB will be reported by the site to the TOID CRC within 72 hours of the site being made aware via the REDCap EDC system. All SAEs will be reported to the TOID CRC via the REDCap EDC system within 24 hours of the site being made aware. Notification of all SAEs will be made to AbbVie by the TOID CRC via email within 24 hours of entry into REDCap.

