APPENDIX E. PROTOCOL AMENDMENT SUMMARY OF CHANGES

Previous Protocol Versions

Protocol	Date
Version 1.0 Initial version.	19-FEB-2021
Version 2.0 Removed washout period of some prohibited medications from eligibility criteria. Added language specifying research labs to be conducted.	12-APR-2021
Version 3.0 Removed rollover to Appendix A Schedule of Events for participants who initiate HCV treatment after Week 12 post-randomization.	22-JUL-2021
Version 4.0 Updated study sites. Clarified secondary endpoints. Clarified study definition of 6 months. Clarified that study screening labs can happen prior to randomization. Clarified study definition of prior HCV treatment. Added timing for participant IDI. Added information for determining participant is lost to follow up. Updated urine toxicology testing requirements. Expanded study visit windows. Added Week 56 visit for participants who do not start HCV treatment by Week 12.	08-MAR-2022
Version 5.1 Updated sample size from 250 to 124. Added language to primary analysis section to clarify updated sample size. Updated primary analysis section to reflect modification of a statistical calculation.	14-DEC-2022

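### Appendix B times all visits for late starters and SOC rollovers from randomization, so it does not supply the treatment-timed assessments that Sections 3.3, 3.4 and 6.2.2 call for

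*Combined protocol and SAP*

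**What the plan says.** **Schedule.** Appendix B covers either arm: "For participants who have not initiated treatment by Week 12 after randomization, complete the following". Its visits are Weeks 12, 24, 36 and 56 after randomization, each -14d/+30d. Every visit has urine toxicology, a dried blood spot, the study survey and the PRO/QOL measures. HCV RNA is marked at Weeks 24 and 56 only, and CMP only in the Week 24 rescreen block for SOC rollovers.

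**Treatment on this schedule.** Section 4.2.9 says that SOC participants still untreated at 24 weeks, if eligible on rescreening, "will be offered HCV treatment at the OTP site via rollover to the Intervention Arm". Appendix B footnote f adds: "If participant is still eligible for rollover to Intervention Arm after rescreening labs result, peer contact to occur weekly", continuing until SVR 12. Appendix B therefore expects people to be treated while they are on it.

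**Endpoints and safety text.**
- Section 3.3(1) defines completion as "taking more than 90% of prescribed treatment course by expected end of treatment date".
- Section 3.3(2) takes SVR12 from an HCV RNA 10 to 36 weeks after end of treatment, by randomized arm.
- Section 3.4(1) assesses substance use at end of treatment and at post-treatment Weeks 12, 24 and 36. It keeps the fixed post-randomization visits for people who do not start treatment.
- Section 6.2.2 says "AEs and SAEs will only be collected from the time of first DAA dose to 30 days after completion of DAA course", for DAA courses in both arms and with no Week 12 cut-off.

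**Which schedule applies.** Appendix A has the treatment-timed visits and is titled as covering all participants. No sentence in the body assigns late starters to either appendix. The contents list describes Appendix B as being for people who do not start treatment, while its current heading adds the Week 12 limit. The amendment log suggests the intent: Version 3.0 "Removed rollover to Appendix A Schedule of Events for participants who initiate HCV treatment after Week 12 post-randomization" and Version 4.0 "Added Week 56 visit for participants who do not start HCV treatment by Week 12".

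**The concern.** Appendix B is triggered by not having started by Week 12, not by never starting. Someone who starts in Week 15 or rolls over in Week 25 appears to stay on visits counted from randomization, while completion, SVR12, substance-use follow-up and adverse events are all defined from treatment dates. Section 6.3 also acts on post-baseline ALT. Appendix A schedules CMP at end of treatment and at post-treatment Week 12, and Appendix B schedules none after the rescreen.

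Follow-up would then be timed differently for early and late starters. More SOC than intervention participants are expected on Appendix B. SVR12 is reported by randomized arm, and Section 7 has no rule that sets rollover data aside, so a difference in measurement could enter between-arm comparisons of secondary and exploratory endpoints.

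**Working it through.** **1. The plan's own figure.** Inputs from Section 7.3.1: 70% versus 40%, 55 completers per group, two-sided alpha 0.05. With a continuity correction, z = [0.30 - 1/55 - 1.96 x sqrt(2 x 0.55 x 0.45/55)] / sqrt((0.21 + 0.24)/55) = (0.2818 - 0.1859)/0.0905 = 1.06, which gives power of 85.5%. Fisher's exact test gives 84.6%. Also 55/0.90 = 61.1, rounded up to 62 per group, or 124 in total. The stated 85% is reproduced. It concerns initiation within 12 weeks, which does not depend on Appendix B.

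**2. Who is on Appendix B at Week 12.** Number = 62 x (1 - initiation rate), assuming the planning rates are Week 12 rates.
- Intervention: 62 x 0.30 = 18.6.
- SOC at 40%: 62 x 0.60 = 37.2, ratio 2.0.
- SOC at 50%: 31.0, ratio 1.67. SOC at 30%: 43.4, ratio 2.33.

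**3. Who then starts late.** The documents give no rate. Assumed late-start shares show the spread:
- Equal shares in both arms: ratio stays 2.0.
- 50% intervention, 25% SOC: 9.3 versus 9.3, ratio 1.0.
- 25% intervention, 50% SOC: 4.65 versus 18.6, ratio 4.0.

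**4. Timing of the SVR test.** For a start in week s and an 8-week course, treatment ends at s + 8 and the SVR window is s + 18 to s + 44. A draw in week v qualifies if v - 44 ≤ s ≤ v - 18.

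| Draw | Qualifying start weeks |
|---|---|
| Week 54 (-14d) | 10 to 36 |
| Week 56 (nominal) | 12 to 38 |
| Week 60.3 (+30d) | 16.3 to 42.3 |

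A draw anywhere in the visit window is sure to qualify only for starts in Weeks 16.3 to 36. The Week 24 draw cannot serve. For a start at Week 12 or later, treatment ends at Week 20 or later, and even the +30d edge (Week 28.3) is at most 8.3 weeks after it. A Week 25 rollover ends treatment at Week 33 and is tested 56 - 33 = 23 weeks later (21 to 27.3 across the window). Appendix A's post-treatment Week 12 visit falls at 10 to 16.3 weeks. A course longer than 8 weeks would move the qualifying start weeks earlier by the difference.

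**5. Substance-use follow-up for the same Week 25 start.** The visits in Section 3.4(1) fall at Week 33 (end of treatment) and Weeks 45, 57 and 69.
- The nominal Week 36 visit is 3 weeks after end of treatment, inside Appendix A's -0d/+30d window.
- The nominal Week 56 visit is 23 weeks after, inside the post-treatment Week 24 window of 22 to 28.3 weeks.
- Post-treatment Week 12 (Weeks 43 to 49.3) and Week 36 (Weeks 67 to 73.3) have no Appendix B visit, since its nearest windows are Weeks 34 to 40.3 and 54 to 60.3.

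The matches are accidental and change with the start date.

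**The case against.** The strongest reply is that the text already covers most of this.

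- **Adverse events.** A reader might infer that adverse events go uncollected in treated rollovers. The documents do not support that: Section 6.2.2 requires collection for any DAA course. What is missing is a schedule row, and adverse-event analysis is mainly descriptive. This stands.
- **Contact during treatment.** A reader might also infer that late starters are not seen while on treatment. Rollovers have weekly peer contact, peers complete adherence surveys at weekly contacts, and Section 4.2.9 gives intervention participants an appointment at the expected end of treatment. This stands for rollovers. For SOC participants who start off-site after Week 12, the plan only says that staff collect progress from the referral site, which is not a scheduled completion record.
- **SVR.** Week 56 meets the protocol's definition for most start dates, and a test at 23 weeks is inside it. This stands. A reader might infer an SVR12 shortfall because late starters have one usable draw and early starters two. That is not supported. The post-treatment Week 36 visit runs from Week 34 to Week 40.3 while the definition closes at Week 36, so the second draw often does not count. The plan also has no rule that missing means failure; Section 7.3.4 names multiple imputation.
- **Which schedule.** Appendix A's title points away from Appendix B for late starters, and the log is only corroboration. If Appendix A does apply, late starters have two competing schedules and the reconciliation is still needed.

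**Conclusion.** The conflict between schedule and text is real and should be fixed. Followed as written, Appendix B cannot reliably supply the end-of-treatment and post-treatment assessments in Section 3.4(1). It leaves off-site late starters without a scheduled completion record, can put the only usable post-treatment RNA outside the SVR window for starts in about Weeks 12 to 16.3 or after Week 36, and delays the SVR test for a Week 25 rollover to about 23 weeks. The later test allows more time for reinfection, which the peer intervention itself aims to prevent.

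The size of any effect between arms is unknown. The group on Appendix B at Week 12 is expected to be about 1.7 to 2.3 times as large in the SOC arm. A reader might carry that ratio over to late starters, but it counts everyone untreated at Week 12, including those who never start. No arm-level bias can be computed from the documents.

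This rests on three assumptions: the planning rates apply at Week 12, courses last 8 weeks, and late starters stay on Appendix B, as its trigger and the log suggest. The primary endpoint, time to initiation (which needs only the start date) and power are unaffected.

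**What to change.** State in the body text which schedule late starters and rollovers follow, and reconcile Appendix B with Sections 3.3, 3.4, 4.2.9, 6.2.2 and 6.3. For anyone starting a DAA after Week 12 in either arm:

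- add the AE/SAE collection line that Section 6.2.2 already requires;
- add an end-of-treatment record of completion and survey;
- time the Week 56 RNA from end of treatment, using Appendix A's post-treatment Week 12 window.

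The absent dispensing entry (against Section 4.2.9) and the absent CMP after rescreening (against Section 6.3) must also be reconciled. Which passage governs is for the sponsor to decide.

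The cost is a schedule amendment, a REDCap branch on treatment start date and one end-of-treatment contact per late starter. Moving the Week 56 RNA adds no draws but gives up these participants' later RNA test, while early starters keep theirs at post-treatment Week 36. Keeping both costs one extra draw.

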3.4 Exploratory Endpoints

- 1) Impact of test and treat versus standard of care referral on proportion of participants with change in substance use assessed by self-reported drug use in the preceding 30 days and urine toxicology at recruitment screening, end of HCV treatment, and post-treatment weeks 12, 24, and 36. Participants who do not start HCV treatment will be assessed at weeks 12, 24, and 36 post-randomization.
- 2) Impact of test and treat versus standard of care referral on subsequent substance use disorder treatment engagement-Proportion of expected weekly OTP visits actually attended, based on participant's OTP treatment plan.
- 3) Proportion of patients in the standard of care arm who are not offered treatment within 6 months (24 weeks) of randomization.
- 4) Proportion of patients in the standard of care arm who do not initiate treatment within 6 months (24 weeks) of randomization and subsequently initiate HCV treatment after study cross over to intervention arm.
- 5) Patient reported outcomes, quality of life measures, and patient satisfaction with test and treat model versus standard of care referral will also be assessed.
- 6) Proportion of participants with grade 3 or greater adverse events (AEs) in test and treat model versus standard of care referral.

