4.2.9 Study Arms

Intervention – Test and Treat strategy: This will consist of a meeting (in person, by phone or over video) with a trained peer mentor who will meet with the study participant after randomization to communicate information about HCV in a manner that takes into account an understanding of experiences with HCV and care access faced by people who use drugs, the potential harms of untreated HCV and the benefits of HCV treatment.

Peer Training, Monitoring, and Quality Assurance. Peers will receive training modelled on our previous experience training peers for HCV treatment support. The training will be provided as modules. Topics to be addressed in the modules are: 1) Power of peer mentoring and key values including confidentiality and respect for all persons; 2) Tools for effective communication; 3) HCV disease and substance use disorder including importance of adherence to medications/visits; 4) Self-care in the peer-mentor role; 5) review of patient tracking tools. Peers will also have an individual training session. Individual sessions will prepare the peer for their peer support role including building communication skills to enhance conversations to support HCV care engagement. Peers will be trained to improve their communication skills with a focus on: 1) providing accurate information; 2) working with patients on goal setting for HCV treatment adherence; and 3) identifying barriers to retention in care. We will ensure peers have demonstrated competency in all of their tasks through knowledge and performance assessments as judged through role-plays.

Peer support and care coordination tasks. Peers will be responsible for maintaining contact with patients in the test and treat arm. They will also complete adherence and food use with medication surveys at weekly contacts. He or she will also communicate the need to return for results of follow up testing and follow through with recommended treatment. The Peer will also communicate to the patient the expected timing of follow up appointments at the drug treatment center and will offer support for the duration of HCV treatment. Up to 15 peers will be enrolled in this study.

The treatment initiation visit at the drug treatment center will depend on the standard amount of time it takes to get results of laboratory testing back to the drug treatment center site. We expect this to be 3-5 days.

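### The rollover rescreen window opens 14 days before the 24-week point, so standard-of-care participants can meet the intervention's peer while exploratory endpoints 3 and 4 still count them as standard of care

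*Combined protocol and SAP*

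**What the plan says.** Section 4.2.9 sets the condition for rollover. It concerns "Participants in the standard of care arm who do not initiate HCV treatment within 6 months (24 weeks) after randomization" who still qualify when rescreened, and it says that they "will be offered HCV treatment at the OTP site via rollover to the Intervention Arm".

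Section 3.4 uses the same 24 weeks twice. Exploratory endpoint 3 is the "Proportion of patients in the standard of care arm who are not offered treatment within 6 months (24 weeks) of randomization". Exploratory endpoint 4 concerns standard-of-care participants with no start in that period who "subsequently initiate HCV treatment after study cross over to intervention arm".

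Appendix B schedules the block "Rescreen for SOC Participants to Rollover to Intervention Arm" (eligibility review, vital signs, concomitant medications, HBsAg, pregnancy test, CBC, CMP, peer contact) only in the column "Week 24 after randomization -14d/+30d". The HCV RNA test is marked in the same column. Footnote f places a peer meeting on the day of the rescreen and continues: "If participant is still eligible for rollover to Intervention Arm after rescreening labs result, peer contact to occur weekly and as needed".

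Neither Appendix B nor its footnotes repeat the 24-week condition. No section says that rollover peer contact must wait for day 168, or how an offer or start between day 154 and day 167 is to be classified.

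**The concern.** A window of two weeks either way is ordinary for surveys and samples. It fits badly on a step that depends on a minimum elapsed time, because the early part of the window falls before anyone can have met the condition.

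The early contact is not incidental. Section 4.2.9 describes the intervention arm in terms of a meeting with a trained peer mentor, and Section 4.1 gives the peers the task of strengthening motivation to start treatment. A standard-of-care participant rescreened on day 154 has therefore received a core part of the intervention with two weeks of the standard-of-care period still to run.

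If that meeting leads the participant to take up the off-site referral before day 168, the resulting offer removes the participant from endpoint 3. A resulting start removes the participant from endpoint 4 and looks like a success of referral. Endpoint 4 is the plan's measure of uptake after crossover, and a closely related proportion appears under Adoption in Table 1. The boundary between the two conditions should therefore be clean.

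**Working it through.** **The plan's own figures.** The plan gives no figure for this overlap. Its one checkable statistical figure, 85% power with 55 completers per group at 70% versus 40% (Section 7.3.1), reproduces at 85.5% with a continuity-corrected normal approximation, and 55/0.90 = 61.1 rounds up to the stated 62 per group. Neither depends on the rescreen window.

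**Day arithmetic** (Appendix B, Section 4.2.9)
- 24 weeks = 24 × 7 = day 168.
- Window opens: 168 − 14 = day 154 (week 22.0).
- Window closes: 168 + 30 = day 198 (week 28.3).
- Width: 198 − 154 = 44 days, of which 14 precede day 168 (14/44 = 32%).

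**What can happen before day 168**
- The peer meeting is on the rescreen date, so as early as day 154. This needs no assumption.
- Weekly peer contact follows once laboratory results are back and the participant is still eligible. Section 4.2.9 says of laboratory turnaround for the intervention arm's initiation visit: "We expect this to be 3-5 days". Assuming the same at rescreen, results arrive on day 157 to 159, which is 9 to 11 days before day 168. Weekly contact could start then if eligibility is read as the laboratory and clinical criteria alone.
- On-site treatment is not available on a straightforward reading, because Section 4.2.9 ties the offer to 24 weeks without a start.

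**What is out of reach.** The primary endpoint closes at 12 weeks = day 84. The rescreen window opens 154 − 84 = 70 days later.

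**How many participants could have early peer contact** (illustrative). Assumptions: 62 standard-of-care participants, the planned 40% uptake taken as the share treated by the rescreen, everyone untreated attends, and visits fall evenly over the 44 days.
- Untreated: 62 × 0.60 = 37.
- Rescreened before day 168: 37 × 14/44 = 11.8, about 12.

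Varying the inputs within the plan's own figures (30% to 50% uptake; 62 per group, or 55 after drop-out):

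| Uptake | Group size | Untreated | × 14/44 |
|---|---|---|---|
| 30% | 62 | 43.4 | 13.8 |
| 40% | 62 | 37.2 | 11.8 |
| 40% | 55 | 33.0 | 10.5 |
| 50% | 55 | 27.5 | 8.8 |

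The even spread is the weakest assumption. If every site books the visit on or after day 168, the number is zero; if sites book early, it is larger.

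**With a window of -0d/+30d** for the rollover block, rescreens fall on days 168 to 198 and the overlap is 0 days.

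**The case against.** The best answer is that a visit window says when procedures may be done and does not waive an eligibility rule. Section 4.2.9 limits the on-site offer to participants with no start in 24 weeks, which cannot be known before day 168, and Section 5.8 prohibits deviations. This stands. A reader might infer from Appendix B that on-site treatment is allowed from about day 157. The documents do not support that: such a start would breach Section 4.2.9. What remains is an inconsistency, since Appendix B lets the rescreen run early, omits the condition and gives no instruction to hold.

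It can also be said that weekly contact depends on the participant being still eligible for rollover, which may be read to include the 24 weeks. That is a fair reading, and on it the certain exposure is one peer meeting. That meeting is not a treatment offer, so by itself it moves nobody out of endpoint 3 or 4. The effect on those endpoints is indirect, through an off-site offer or start that the meeting prompts.

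Finally, endpoints 3 and 4 are exploratory and describe the standard-of-care arm only. That limits the weight of the point, but does not answer it.

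**Conclusion.** The point holds for peer contact and for the timing of the eligibility review: both can occur up to 14 days inside the period that Section 4.2.9 and exploratory endpoints 3 and 4 treat as standard of care. On the assumptions shown, about 12 standard-of-care participants would be affected, or roughly 9 to 14 across the plan's own uptake and drop-out figures. Starts between weeks 12 and 24 would lower the number, because the 40% was used to size a 12-week endpoint.

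A reader might go further and compute an inflated 24-week uptake in the standard-of-care arm from early on-site starts. The documents do not support such a figure. It would rest on starts that Section 4.2.9 excludes, and 24-week uptake is not itself an endpoint. The number of misclassified offers or starts cannot be derived.

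The scope is mainly exploratory endpoints 3 and 4. A small effect on time to initiation is possible if early peer contact prompts an off-site start. The lack of a stated censoring rule at rollover is a separate matter, which also arises after day 168. The primary endpoint and sample size are unaffected. This is a worthwhile correction, not a threat to the trial's main result.

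**What to change.** Reconcile Appendix B and footnote f with Section 4.2.9. One way is to give the rollover block its own window that does not open before the 24-week point, for example -0d/+30d, which Appendix A already uses for End of Treatment. The block should include the eligibility review, the rescreen laboratory tests, the HCV RNA result used for eligibility (undetectable RNA is an exclusion in Section 5.1) and the footnote f peer meeting. The Week 24 surveys, toxicology and dried blood spot can keep -14d/+30d. The 24-week condition should be repeated in footnote f, so that the schedule and Section 4.2.9 say the same thing.

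The change is confined to Appendix B and its footnote. A participant seen early for surveys would have the rescreen up to 14 days later, which can be at a regular OTP visit (Section 4.2.12), and may need a second blood draw. The sample size and primary analysis do not change.
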